This proof-of-concept study has been reviewed and granted a waiver of informed consent for all subjects enrolled by the Human Research Protection Office at Washington University in St. Louis (HRPO#201901180) and is registered at clinicaltrials.gov (NCT04020887). It is infeasible to conduct this proof-of-concept study without a waiver of consent. Additionally, this study has been determined to involve no more than minimal risk to participants, as study participation would not deviate from or delay current standards of peri-anesthesia care. Both the “Good ReseArch for Comparative Effectiveness” (GRACE) checklist⁷ and PICOTS framework⁸ (Table 1) were used in designing this study.

The conduct and reporting of this observational study will follow the “Reporting of studies Conducted using Observational Routinely-collected health Data” (RECORD)⁹ statement and the “Strengthening the Reporting of Observational Studies in Epidemiology” (STROBE)¹⁰ statement guidelines for reporting observational studies.

[figure not shown]
Table 1. PICOTS Framework

PICOTS typology for a comparative effectiveness research protocol	
Population	Adult (18 years and older) patients undergoing elective surgery
Intervention	Telemedicine center for PACU
Comparator	Current post-anesthesia care unit practice
Outcomes	(i) potential utility, and (ii) acceptability of integrating telemedicine in the post-anesthesia care unit environment
Timing	6-month study duration

Setting	Hospital environment – Barnes-Jewish Hospital, St. Louis, Missouri
---------	--

Primary Intervention: Telemedicine Center for PACU

Two bays in Barnes Jewish Hospital (BJH) in St. Louis, Missouri, will be equipped for telemedicine interaction (Figure 1). Video cameras and monitors have been installed in each of these bays to allow for remote monitoring, as well as two-way video communication during the interaction phase. The telemedicine center is staffed by attending anesthesiologists along with certified registered nurse anesthetists (CRNAs), anesthesiology residents, and student registered nurse anesthetists (SRNAs), and is currently providing evidence-based support to clinicians in the operating rooms.^{11–14}

Two PACU bays located across from nurse's station

High-resolution camera for patient monitoring and communication

Ultra-sharp monitor on telescoping arm for two-way patient communication

High-definition microphone for patient monitoring and communication

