We will conduct focus groups with stakeholders to gain insights regarding their perceptions of barriers and facilitators related to the above-noted PACU functions before and after the implementation and use of a telemedicine center for the PACU. We will also gather perspectives from the stakeholders on the role and impact of the telemedicine center on their individual and team workflows in the PACU and between units during care transitions. Focus group participants will include nurses, anesthesiologists, surgeons, hospital administrators, and PACU telemedicine center clinicians. Our focus groups will be homogeneous in order to understand the clinician workflow based on their professional role, and their use of the telemedicine center in supporting their role and responsibilities. Each focus group will comprise five to six participants. This will allow in-depth discussions of the workflow problems and unintended

consequences caused by the implementation and use of the telemedicine center for the PACU. The focus group sessions will be guided by a semi-structured interview guide focused on the following themes: (1) PACU core functions, (2) PACU patient workflow, (3) PACU clinician activities and tasks, (4) tools and technologies used to support the PACU workflow, (5) major barriers to PACU functions, (6) use of a telemedicine intervention as a potential mechanism to support effective and efficient functioning of the PACU. We plan to conduct 6-8 focus group sessions (4 pre-intervention during observation phase, and 4 post-intervention during interaction phase) or until data saturation is attained.

Study Size

Patients are allocated to PACU bays according to the discretion of the nurse in charge of the PACU. Currently, approximately two patients per day are cared for in each bay in the participating PACU. Therefore, the telemedicine team will monitor approximately four patients per day over the course of the proof-of-concept study. We estimate that 500 patients will be included in this proof-of-concept study (250 per monitored phase) (Figure 4).

[figure not shown]

Figure 4. Allocation of sample size and PACU layout for proof-of-concept study

Statistical Methods

Primary Outcome

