This is a proof-of-concept study and will only address surrogate outcomes. The primary outcome (time to PACU discharge readiness) will use two comparison groups. First, historical controls will be drawn from the observation phase. A propensity score for inclusion into the study will be generated as a function of (minimally) surgery performed, day of week, time of day, age, and sex. 3:1 matched control patients will be included. The outcome will be analyzed with interrupted time series methods with flexible functions of calendar time used to adjust for secular trends; the study hypothesis is a non-zero discontinuity at telemedicine implementation.

That is, if Y_i is the outcome for the i th patient at time t_i with covariate vector X_i , while the implementation time is t_0 , and $I()$ is the indicator function,

$$Y_i = f_1(t_i)I(t_i < t_0) + f_2(t_i)I(t_i \geq t_0) + X_i\beta + \epsilon H_0: f_1(t_0) = f_2(t_0)$$

where f_1 and f_2 are smooth functions. Other patient factors known to strongly influence PACU length of stay (age, ASA physical status, number of co-morbidities, morbid obesity, obstructive sleep apnea, surgical specialty, primary anesthesia type, history of postoperative nausea and vomiting, preoperative pain, and scheduled case duration) will be included as covariates. The minimization criteria will be least squares or trimmed least squares or other robust criteria if there are substantial outliers. Outcomes will be examined for residual auto-correlation, and if non-negligible, auto-correlation robust standard errors (such as Newey-West errors) and an ARIMA model will be reported. Confidence intervals will be generated by non-parametric bootstrap sampling where possible. No adjustment will be made for matching, but bootstrap methods will respect the matched “units.” P-values will be generated both by likelihood ratio tests and by using non-deployment times as a null distribution; that is, we will run the same analysis looking for discontinuity at times remote from the true implementation time. We will conduct sensitivity analyses with transformations of the outcome variable. We will use an excluded run-in period of 1 month as a sensitivity analysis. Because hospital length of stay is unlikely to be meaningfully affected by a telemedicine center for the PACU, but does track overall acuity and surgical severity, we will use hospital length of stay as a control time series.

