Contemporaneous control patients will also be gathered. A propensity score for study inclusion will be generated as a function of (minimally) surgery performed, calendar time, time of day, age, and sex. 3:1 matched control patients will be included. Differences will be analyzed by t-tests using permutation calibration. Confidence intervals on the difference in mean time to discharge readiness will be generated by nonparametric bootstrap. We will include a sensitivity

analysis where the interrupted time series method includes historical and contemporaneous control patients with the treatment indicator T for study patients,

$$Y_i = f_1(t_i)I(t_i < t_0) + f_2(t_i)I(t_i \geq t_0) + X_i\beta + T_i + \epsilon.$$

Based on data from our EHR, patients are currently in PACU for a mean of 150 min (standard deviation = 65 min) before they are determined to be suitable for discharge. Based on these values, with 250 patients in each phase (observation and interaction), this observational before and after study will have >70% power with an alpha <0.005 and > 90% power with an alpha <0.05 to detect a mean decrease in 20 min (from 150 min to 130 min) to PACU discharge readiness time. Statistical testing will be with appropriate statistical software. Using non-parametric bootstrap of historical data and a 3:1 control sampling ratio, the average standard error on the difference in means under the null hypothesis was 5.5 minutes, giving an anticipated 95% confidence interval width of 22 minutes. A somewhat larger standard error will be encountered when adjusting for covariates or secular trends; however, this suggests that we will be able to resolve differences in PACU readiness times of 20-25 minutes. This difference of approximately a third a standard deviation is usually regarded as a “small-moderate” sized effect.

Secondary Outcomes

Hand-off quality assessment from the PACU nurse binary survey response will be analyzed using a logistic regression model adjusting for surgical service, age, and sex. Because observation resources are required for hand-off evaluations, no matching will be performed, and no contemporaneous controls will be gathered. Adjusted differences in rates of inadequate hand-off will be summarized with 95% confidence intervals and model-based p-values.

Observed reported hand-off communication quality will be presented as a purely descriptive result.

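### The contemporaneous comparison for the primary outcome has no before/after contrast, so it cannot separate a standing difference of the two study bays from a telemedicine effect

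*Combined protocol and SAP*

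**What the plan says.** Statistical Methods, Primary Outcome, gives time to PACU discharge readiness two comparison groups.

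- **Historical controls.** These are analysed by interrupted time series, for which "the study hypothesis is a non-zero discontinuity at telemedicine implementation".
- **Contemporaneous controls.** Selection is by matching: "A propensity score for study inclusion will be generated as a function of (minimally) surgery performed, calendar time, time of day, age, and sex", then "3:1 matched control patients will be included". The test is one sentence: "Differences will be analyzed by t-tests using permutation calibration". The estimate is a plain mean difference: "Confidence intervals on the difference in mean time to discharge readiness will be generated by nonparametric bootstrap". No phase, baseline difference or phase-by-group term is given, and the permuted label is not named.
- **Pooled sensitivity analysis.** This is an "analysis where the interrupted time series method includes historical and contemporaneous control patients with the treatment indicator T for study patients". T enters as a main effect only.

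On how patients reach the study bays, Study Size says: "Patients are allocated to PACU bays according to the discretion of the nurse in charge of the PACU". The bay figure under Primary Intervention carries the label "Two PACU bays located across from" the nurse's station, and the same section describes the cameras and monitors installed there. In the observation phase the telemedicine center already watches these bays but does not communicate with PACU staff unless there is a patient safety event.

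**The concern.** A two-group comparison of study-bay patients with matched patients elsewhere attributes to telemedicine whatever distinguishes the two bays after matching. Placement is discretionary, and the bays differ in location and equipment. The named matching variables do not describe any of these directly. If readiness times in the two bays already ran shorter than in matched controls, a significant result could appear without any telemedicine effect. If they ran longer, a real effect could be diluted.

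The study has the data to check this. The observation phase shows how the same bays compare with matched controls when there is no interaction. As written, the contemporaneous analysis does not use it. The comparison yields its own p-value and interval for the primary outcome, and the plan has no rule for reconciling it with the time-series result.

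**Working it through.** **Inputs from Statistical Methods, Primary Outcome.** SD 65 min; 250 patients per phase; target difference 20 min; 3:1 controls; bootstrap standard error (SE) under the null 5.5 min; 95% interval width 22 min; more than 90% power at alpha 0.05 and more than 70% at 0.005. Two-sided testing is my assumption, because sidedness is not stated.

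**The plan's own figures.**
- SE for 250 v 250 = 65 × √(2/250) = 5.81 min. Power for 20 min = Φ(20/5.81 − 1.96) = 93%, and Φ(20/5.81 − 2.81) = 74% at alpha 0.005.
- Interval width = 2 × 1.96 × 5.5 = 21.6 min, which rounds to 22.

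These figures reproduce.

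**What the test can reject.** Let b be the bay difference left after matching and δ the telemedicine effect. In the interaction phase the study-minus-control mean difference estimates b + δ. Permuting study/control labels gives the reference distribution for b + δ = 0, so calibration handles chance but not b.

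**Illustration with δ = 0.** The documents give no value for b; the values below are assumed. Rejection = Φ(−1.96 + b/SE) + Φ(−1.96 − b/SE). SE is the plan's 5.5 min, or 65 × √(1/250 + 1/750) = 4.75 min.

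| b (min) | SE 5.5 | SE 4.75 |
|---|---|---|
| 0 | 5% | 5% |
| 2 | 6.5% | 7.1% |
| 3.5 | 9.75% | 11.4% |
| 5 | 14.9% | 18.4% |
| 10 | 44.4% | 55.8% |

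Exact doubling to 10% needs b = 3.59 min at SE 5.5 and 3.10 min at SE 4.75. A simulated within-set permutation test (250 sets of 1:3, gamma outcomes with mean 150 and SD 65, 4,000 runs) rejected in 4.9% at b = 0 and 11.7% at b = 3.5.

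**If both phases are pooled**, which the wording does not exclude, half of the study patients had no interaction. The SE is 65 × √(1/500 + 1/1500) = 3.36 min, or 5.5/√2 = 3.89 min, and b = 3.5 gives 18.1% or 14.7%.

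**Dilution.** If a 20 min reduction is offset by bays running 5 min longer, 15 min remain. Power is Φ(15/5.5 − 1.96) = 78% instead of 95%, or Φ(15/4.75 − 1.96) = 88% instead of 99%.

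**The pooled sensitivity model.** There are two readings of T.
- T marks study patients in both phases. It then absorbs a constant bay difference, but the jump from f1 to f2 is common to study and control patients.
- T marks only interaction-phase study patients. Because f2 is free, T is then identified from the post-implementation study-versus-control contrast alone, which is b + δ again.

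Neither reading isolates δ. That would need a T-by-phase term.

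**Phase-difference contrast.** (Study − control, interaction) − (study − control, observation) = (b + δ) − b = δ if b is constant. Its SE is √2 times larger: 5.5 → 7.8 min, or 4.75 → 6.7 min. Power for 20 min is Φ(20/7.78 − 1.96) = 73%, or Φ(20/6.71 − 1.96) = 85%. In simulation with constant b it rejected in 4.1%, 3.6% and 4.9% at b = 0, 3.1 and 3.5 (1,500 runs each).

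**The case against.** Much of the case on the other side stands.

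- **The label is inferred.** The plan names neither the permuted label nor the phase. Study versus control is the natural reading given a study-inclusion score, matching on calendar time and a simple mean difference, but it remains a reading.
- **A reader might infer that the test addresses the wrong hypothesis altogether.** The documents do not support that. The discontinuity hypothesis is written for the time series. The contemporaneous comparison has its own estimand, and the PICOTS table names current PACU practice as the comparator, which concurrent controls fit. The null also contains the telemedicine effect; it is not only a statement that the bays are alike. The test asks a legitimate question in a confounded form.
- **A reader might infer that the plan's false-positive rate is doubled.** This is not shown. No bay-specific times are given, and 3.5 min is a value chosen for illustration.
- **Evidence for a bay difference is indirect.** The covariate list is a minimum, so the score may hold more. Discretionary placement may work partly through surgery type and time of day, which are matched. The location is a figure label with no stated effect. Nurse forms are filled in after discharge, so completing them cannot directly delay that patient's readiness time.
- **Partial disclosure.** The limitations section says that improvements cannot be causally attributed and that clinicians will know of the initiative. That is a general caveat about the before-and-after approach. It does not address a comparison that has no before.

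What survives is structural: neither the planned test nor the sensitivity model can separate b from δ, although the observation phase could supply the missing contrast. The interrupted time series does target a change at implementation, so the point is confined to the contemporaneous comparison.

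**Conclusion.** The point holds as a limitation of one of the two primary-outcome comparisons. On the natural reading, a significant contemporaneous result may reflect a standing bay difference, a telemedicine effect or both, and nothing specified for that comparison distinguishes them. The size depends wholly on an unknown residual difference: about 10-11% rejection at 3.5 min and 15-18% at 5 min, assuming no telemedicine effect, two-sided 5% testing, an SE of 4.75 to 5.5 min and interaction-phase patients only.

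A reader might also infer that a phase-difference test would guarantee nominal error. It would not. Its error rate near 5% rests on a bay difference that stays constant across phases, and nothing in the documents ensures this if placement or behaviour shifts once interaction begins. Replacing the planned test outright is therefore a trade-off. Adding the missing contrasts beside it is a cheap improvement that should be made.

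**What to change.** In Statistical Methods, Primary Outcome (contemporaneous controls):

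1. State that the t-test uses interaction-phase study patients and that study-versus-control is the permuted label.
2. Draw the 3:1 matched contemporaneous controls separately within the observation phase and the interaction phase.
3. Report the observation-phase study-minus-control difference with its interval, as a no-intervention check on the bays.
4. Report the interaction-minus-observation difference of these contrasts beside the planned t-test, resampling or permuting whole matched sets.
5. State that a significant single-phase result will not be attributed to telemedicine unless the phase-difference estimate supports it.

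**Cost.** SAP wording and an extra EHR extraction for observation-phase controls; no new patients.

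**Downsides.** The phase-difference estimate is less precise: SE 7.8 min and 73% power for 20 min at the plan's SE, or 6.7 min and 85% at SD 65. The difference detectable with 80% power is 7.78 × (1.96 + 0.84) = 21.8 min, or 6.71 × 2.80 = 18.8 min. The contrast removes only a bay difference that is constant across phases. It also subtracts any effect of the remote monitoring already present in the observation phase, so it estimates the effect of interaction over and above monitoring.

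### The stated >90% and >70% power is for an unadjusted difference in means; no power or standard error is given for the discontinuity test that the before-after analysis specifies

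*Combined protocol and SAP*

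**What the plan says.** All of this is in the combined protocol and SAP, Statistical Methods, Primary Outcome.

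- Two analyses: "The primary outcome (time to PACU discharge readiness) will use two comparison groups".
- Before-after analysis: an interrupted time series with "flexible functions of calendar time used to adjust for secular trends"; "the study hypothesis is a non-zero discontinuity at telemedicine implementation". The model has separate smooth functions f1 and f2 before and after implementation time t0, and the null hypothesis is f1(t0) = f2(t0). The degree or stiffness of f1 and f2 is not given. Covariates are added, described as "Other patient factors known to strongly influence PACU length of stay". On intervals: "Confidence intervals will be generated by non-parametric bootstrap sampling where possible".
- Contemporaneous controls: "Differences will be analyzed by t-tests using permutation calibration".
- Power: from a mean of 150 min, an SD of 65 min, 250 patients per phase and a 20-minute fall in the mean, "this observational before and after study will have >70% power with an alpha <0.005 and > 90% power with an alpha <0.05".
- Precision: with 3:1 control sampling from historical data, "the average standard error on the difference in means under the null hypothesis was 5.5 minutes", which the plan turns into a 95% interval about 22 min wide. It then notes, without a figure, that adjusting for covariates or trends will raise the SE to some extent, and concludes that differences of 20-25 min can be resolved.

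**The concern.** The power sentence is attached by name to the before-after study, but its inputs are those of a two-sample comparison of means. The before-after hypothesis is a different quantity: the gap between two fitted curves at the point where one ends and the other begins. A curve is estimated least precisely at its end, so this gap has a larger SE than a difference in means from the same patients. The planned covariates work in the other direction, but the plan does not say how much variance they explain.

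What is at stake is how a non-significant discontinuity would be read. Set against a stated power above 90%, it would look like good evidence against a 20-minute reduction. The plan does not show that the specified test can support that inference.

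**Working it through.** **Inputs from the plan.** SD 65 min; difference 20 min; 250 per phase; alpha 0.05 and 0.005 (taken as two-sided); bootstrap SE 5.5 min.

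**Step 1: reproduce the plan's figures.** SE = 65 × √(1/250 + 1/250) = 5.81 min; 20/5.81 = 3.44. With the noncentral t on 498 degrees of freedom, power is 93.0% at alpha 0.05 and 73.2% at alpha 0.005, matching >90% and >70%. Interval width: 2 × 1.96 × 5.5 = 21.6, about 22 min. Both follow from a plain difference in means.

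**Step 2: the largest SE that gives the stated power.** For 90% at alpha 0.05: 20/(1.960 + 1.282) = 6.17 min, and 6.17/5.5 = 1.12. For 70% at alpha 0.005: 6.00 min.

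**Step 3: SE of the discontinuity, as an illustration.** Assumptions not in the plan: a straight line on each side of t0, even accrual in time, independent errors. With time scaled to [0, 1] on one side, the variance of the fitted value at the boundary is

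σ² × [1/n + (1/2)²/(n/12)] = σ² × (1/n + 3/n) = 4σ²/n.

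The SE is therefore twice that of a mean, on each side and for the difference. It does not depend on the length of the window. Covariates unrelated to time multiply it by √(1 − R²).

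The pre-period number can be read in more than one way (250 monitored patients; 750 matched controls; or both together), so several are shown. R² values are assumed. Power is for 20 min at two-sided alpha 0.05.

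| Pre/post patients | Plain SE | Jump SE, R² = 0 | Power, R² = 0 | R² = 0.3 | R² = 0.5 | R² needed for 90% |
|---|---|---|---|---|---|---|
| 250/250 | 5.81 | 11.63 | 40% | 54% | 68% | 0.72 |
| 750/250 | 4.75 | 9.49 | 56% | 71% | 85% | 0.58 |
| 1000/250 | 4.60 | 9.19 | 59% | 74% | 87% | 0.55 |
| unlimited/250 | 4.11 | 8.22 | 68% | 83% | 93% | 0.44 |

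The last column is 1 − (6.17/jump SE)²; for example, 1 − (6.17/11.63)² = 0.72. The last row is a limit: even if f1(t0) were known exactly, the 250 post-implementation patients leave 2 × 65/√250 = 8.22 min.

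At alpha 0.005, the first three rows give 14-26% at R² = 0 and 22-60% at R² 0.3-0.5, against >70% stated.

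**Step 4: start from the plan's own SE.** The plan's 5.5 min is larger than the plain 4.75 at 750/250, so the table does not derive from it. Doubling 5.5 gives 11.0 min: power 44% with no covariate gain, 58-73% at R² 0.3-0.5, and R² = 1 − (6.17/11.0)² = 0.69 needed for 90%.

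**Step 5: the 20-25 min statement.** For the contemporaneous-control t-test at SE 5.5: Φ(20/5.5 − 1.96) = Φ(1.68) = 95%. For the discontinuity with linear trends at R² 0.3-0.5, power for 25 min over the first three rows is 73-97%.

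**Sensitivity to trend form.** Separate quadratics triple the plain SE (17.4 min at 250/250). A stiffer or penalised smooth lies between the plain and linear cases. Residual autocorrelation, which the plan anticipates, is not in these figures.

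**The case against.** The plan is partly open about this. It labels the 5.5 min as the SE of a difference in means, warns that adjustment will increase it, and offers the 20-25 min only as something the figure suggests. That stands as disclosure. But the warning follows the bootstrap SE and does not qualify the power sentence before it. It also gives no size, where the room for 90% power is 12%.

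The replacement figures rest on a trend form and R-squared that the plan does not state. That is right, and they show direction and scale only. Three stronger readings should be resisted:

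- **That the sponsor miscalculated.** The stated power, and the interval width derived from the 5.5-minute SE, both reproduce.
- **That the true power is some particular low value, or that 90% is out of reach.** Strong covariates, a longer pre-period series or a penalised smooth could bring the SE close to what is needed. The plan does not give enough to say.
- **That the 20-25 min statement is wrong.** It is supported for the contemporaneous-control t-test, and 25 min is plausible for the discontinuity under linear trends with moderate covariate gain.

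On weight: Study Size derives the 500 patients from bay throughput, not power. The study is a proof of concept, and its limitations section disclaims causal attribution. No enrolment or stopping decision depends on the figure. This limits the consequence to interpretation. The plan does not say that a null result would be read from the power, and it already intends bootstrap intervals.

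**Conclusion.** The point holds as a mismatch between the basis of the power and the specified test, not as an arithmetic error. That the >90% and >70% figures are those of an unadjusted difference in means, and that nothing is stated for f1(t0) − f2(t0), follows from the document with no outside assumption.

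The size is conditional. With separate linear trends, even accrual and independent errors, 90% power for 20 min would need the covariates to explain roughly 55-72% of the variance at the allocations considered, or about 44% with unlimited pre-period data. More flexible trends need more; stiffer ones need less. Ninety per cent power for 20 min is therefore not shown for the before-after test, although it is not ruled out. The paragraph should be corrected before results are interpreted against it.

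**What to change.** In the power paragraph of Statistical Methods, Primary Outcome:

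1. State that the >90% and >70% power and the 5.5-minute SE apply to an unadjusted difference in means.
2. Replace the unquantified remark about a larger SE with the SE, power and interval width for f1(t0) − f2(t0). Obtain them by rerunning the existing historical-data bootstrap with the planned trend terms, covariates and control ratio, and state the assumptions on each.
3. Limit the 20-25 min statement to the contemporaneous-control t-test, unless the rerun supports it for the discontinuity.

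The cost is one rerun of an analysis the sponsor already has and new wording for one paragraph. The sponsor must commit to a working form for f1 and f2, and the stated power for the before-after comparison will probably look less favourable. There are no extra patients and no change of estimand.

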After the completion of the hand-off procedure, the PACU nurse who interacted with the telemedicine center clinicians will complete a short survey to assess the telemedicine center's involvement in that patient's transfer of care.

The successful integration of the telemedicine center clinicians' hand-off activity will be measured in the following way:

Hand-off activity – Success will be measured (in the interaction phase) by the ability of the telemedicine center clinicians to join and contribute meaningfully to the hand-off discussion. The impact of the telemedicine center clinicians on this key function will be determined from feedback from key stakeholder focus groups (see *Aim 2*) and PACU nurse surveys. These stakeholders will comment on utility of the telemedicine center's involvement and provide suggestions for improvement. A binary assessment of hand-off

adequacy will be provided by the PACU nurse hand-off survey. The telemedicine center clinician will use a hand-off content checklist to record the number of mandatory items not discussed and number of recommended non-mandatory items discussed. For each of the observation and intervention phase, for 50 randomly selected cases a trained observer (not the participant in hand-off) will use the hand-off communication assessment tool of Weinger and others¹⁶ substituting the telemedicine center hand-off content checklist. A run-in phase of 1 month during the intervention will elapse before any of the 50 detailed communication evaluations are performed.

Aim 2 – Identify barriers to and facilitators for the implementation of a telemedicine center for the PACU, as perceived by key stakeholders

We will assess the attitudes of key stakeholders in order to identify barriers to and facilitators for implementation of a telemedicine center for the PACU. (Figure 3)

Stakeholder Focus Groups

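### The hand-off survey analysis makes no allowance for repeated ratings by the same nurse, so the interval and p-value for the difference in inadequate hand-off rates may be invalid

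*Combined protocol and SAP*

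**What the plan says.** Under Hand-off Activity, once a hand-off is over, "the PACU nurse who interacted with the telemedicine center clinicians will complete a short survey". A yes/no rating of hand-off "adequacy will be provided by the PACU nurse hand-off survey". Each data point is therefore one nurse's opinion of one hand-off.

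Under Statistical Methods, Secondary Outcomes, these ratings are "analyzed using a logistic regression model adjusting for surgical service, age, and sex", and the result is reported as follows: "Adjusted differences in rates of inadequate hand-off will be summarized with 95% confidence intervals and model-based p-values". For this outcome "no matching will be performed, and no contemporaneous controls will be gathered", so the difference can only be between the observation and interaction phases. Study phase is not itself listed among the model terms.

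Study Size expects about 500 patients, 250 in each phase, and notes that "approximately two patients per day are cared for in each bay in the participating PACU", or about four a day over the two bays.

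For this outcome the document mentions no nurse identifier, nurse random effect, GEE, cluster-robust error or cluster bootstrap. It does allow for dependence or robust variance elsewhere: Newey-West errors and a bootstrap that keeps matched units together for the primary outcome, and a robust standard error for the difference in discharge-ready times.

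**The concern.** Nurses differ in what they call an adequate hand-off, so two ratings by one nurse are likely to be more alike than ratings by two nurses. All three listed covariates describe the patient or the surgery; none describes the rater. Model-based inference from an ordinary logistic regression counts each survey as a separate piece of information.

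At stake is whether the 95% interval has its stated coverage and whether the p-value means what it says. This is the only hand-off result with formal inference, since the observer-rated communication quality is to be purely descriptive. An apparent improvement could reflect which nurses happened to be on duty in each phase, or a few nurses who took strongly to the telemedicine contact, and the reported interval would not show that uncertainty.

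**Working it through.** **The plan's own figures.** None is given for this outcome: no event rate, standard error, power, number of nurses or within-nurse correlation. The only power statement concerns the primary outcome, and it reproduces. SE = 65 × √(2/250) = 5.81 min and 20/5.81 = 3.44, so power is 93.1% at two-sided 0.05 and 73.7% at 0.005, against the stated >90% and >70%. It does not bear on the hand-off analysis.

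**Are raters repeated?** If every patient yields a survey, avoiding repeats would need 250 different nurses in a phase. Two bays taking about four patients a day reach 250 patients in 250/4 = 62.5 days. Even 40 nurses would average 250/40 = 6.25 surveys each.

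**Inputs.** From the document: 250 patients per phase, taken as the upper bound on surveys. Assumed: J = 10 to 40 nurses per phase; within-nurse ICC 0.02 to 0.20; correlation ρ of a nurse's rating tendency between phases of 1, 0.5 or 0, where ρ = 0 also represents different nurses in each phase.

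**Formula for the planned contrast.** With m = 250/J surveys per nurse per phase, evenly spread, the variance of the phase difference relative to independence is

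DE = 1 + (m − 1) × ICC − ρ × m × ICC.

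For ρ = 1 this reduces to 1 − ICC. The true SE is √DE times the model-based SE, and the real error rate of a nominal 5% test is 2 × (1 − Φ(1.96/√DE)).

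Worked example, J = 20 (m = 12.5) and ICC 0.05:
- ρ = 1: DE = 1 − 0.05 = 0.95
- ρ = 0.5: DE = 1 + 11.5 × 0.05 − 0.5 × 12.5 × 0.05 = 1.26
- ρ = 0: DE = 1 + 11.5 × 0.05 = 1.58

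SE ratio, with real type I error in brackets:

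| Nurses, ICC | Same nurses, stable habits (ρ = 1) | ρ = 0.5 | Different nurses (ρ = 0) |
|---|---|---|---|
| 40, 0.02 | 0.99 (4.8%) | 1.02 (5.5%) | 1.05 (6.2%) |
| 20, 0.05 | 0.97 (4.4%) | 1.12 (8.1%) | 1.25 (11.8%) |
| 40, 0.20 | 0.89 (2.8%) | 1.19 (10.1%) | 1.43 (17.1%) |
| 10, 0.20 | 0.89 (2.8%) | 1.82 (28.1%) | 2.41 (41.6%) |

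Setting DE = 1 gives ρ = 1 − 1/m. With even staffing, the ordinary SE is therefore large enough only if ρ is at least 0.84 (40 nurses), 0.92 (20) or 0.96 (10).

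**Simulation check.** An unadjusted logistic Wald test of phase was simulated with 20% inadequate hand-offs (assumed), 4,000 replicates, nurses assigned at random, 10 to 40 nurses and ICC 0.05 to 0.20 on the latent logit scale. Type I error was 4.2% to 5.4% with the same nurses and stable habits, 6.2% to 21% at ρ = 0.5, and 6.9% to 31% with different nurses. The pattern is the same; the sizes are smaller at the top because the ICC is on a different scale.

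**If only interaction-phase surveys exist.** The estimate is then a single rate, with DE = 1 + (m − 1) × ICC. For 40 nurses and ICC 0.05, DE = 1 + 5.25 × 0.05 = 1.26 (SE ratio 1.12, effective sample 250/1.26 = 198). For 10 nurses and ICC 0.20, DE = 1 + 24 × 0.20 = 5.8 (SE ratio 2.41, effective sample 250/5.8 = 43).

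**The case against.** A reader might infer that the standard errors are simply wrong, and too small. The documents do not support that. The planned quantity is a difference between consecutive three-month phases in the same two bays, so substantial overlap of staff is plausible. If the same nurses rate in similar proportions with unchanged habits, their tendencies largely cancel and the ordinary SE is about right or slightly too large. That stands. It needs more than shared staff, however: habits must also be almost unchanged between phases. The intervention is a personal interaction rated by unblinded nurses, and the limitations section accepts that awareness of the initiative could alter behaviour.

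A reader might also apply the effective sample of 43 to 198 to the planned result. Those figures belong to a single rate, and Secondary Outcomes describes a difference. They become relevant only if there are no observation-phase surveys, which Hand-off Activity leaves unclear: the survey goes to the nurse who interacted with the center, success is measured in the interaction phase, and in the observation phase the center does not communicate with PACU clinicians except for a safety event.

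It is also fair that repeated rating by the same nurses is an inference, that neither the nurse count nor the ICC is given, and that this is one secondary outcome of a proof-of-concept study that already disclaims causal attribution. These points limit the consequence. They do not supply a valid interval.

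**Conclusion.** The gap is real: a rater's opinion, almost certainly given repeatedly by a limited group of nurses, is analysed as if every rating were independent. The interval and p-value for the adjusted difference may be invalid, but neither the direction nor the size of the error can be fixed from the documents. Over the assumed range the true SE lies between 0.89 and 2.41 times the model-based one. It is near or just below 1 with shared, stable raters, and above 1 when staffing or nurses' reactions differ by phase. If surveys exist only in the interaction phase, the interval for that single rate is too narrow by a factor of about 1.1 to 2.4 for ICC 0.05 to 0.20. The primary analysis is unaffected. This is a cheap improvement to a secondary outcome, worth making before data collection because a missing rater identity may not be recoverable later.

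**What to change.** Record a coded nurse identifier with every hand-off survey. Keep the planned covariates, and replace the model-based inference with one of the following, chosen in advance:
- GEE, or the same logistic model with cluster-robust standard errors by nurse, with a small-sample correction; or
- a mixed logistic model with a nurse intercept and nurse-by-phase variation. A nurse intercept alone is not enough, because it assumes that every nurse's tendency carries over unchanged between phases and can still understate the SE of the phase difference.

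Report the number of nurses, how many rated in both phases, and the estimated ICC. In the same edit, state whether surveys are collected in the observation phase, and name study phase as a model term if they are.

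The cost is one coded field and a different variance option. An identifier, even coded, may make ratings slightly less candid. If there are very few nurses, say about 10, cluster-based inference is fragile even after correction. The interval may be wider, though it need not be if the same nurses rate in both phases.
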